## Research Protocol: Healthy Lifestyle Prenatal Care Study

### Aims:

**Specific Aim 1.** Use a RCT to evaluate the short- and more long-term efficacy of the COPE-P program to improve healthy lifestyle behaviors (nutrition and exercise), psychosocial health, and birth and post-natal outcomes in pregnant emotionally distressed minority women as compared to an attention control group.

**Hypotheses 1a (primary outcomes).** Immediately after the COPE-P program, at 4-6 weeks postpartum (3 months post intervention), and at 6 months postpartum (8 months post intervention), COPE-P participants will report higher healthy lifestyle behaviors, and less anxiety, stress and depressive symptoms than will the attention control participants.

**Hypothesis 1b (secondary outcomes).** COPE-P participants will demonstrate more appropriate pregnancy weight gain, better birth outcomes (mode of delivery, birth weight, and gestational age), more appropriate postpartum weight loss, and better breastfeeding outcomes than attention control participants.

**Specific Aim 2.** Examine the role of cognitive beliefs and perceived difficulty in leading a healthy lifestyle in mediating the effects of the COPE-P program on healthy lifestyle behaviors and psychological symptoms in minority pregnant women.

**Hypothesis 2 (theory building exploratory).** The effects of the COPE-P program on participants' healthy lifestyle behaviors and levels of anxiety, stress and depressive symptoms will be mediated by beliefs about their ability to make healthy lifestyles choices and their perceived difficulty in leading a healthy lifestyle.

**Exploratory Aim.** Explore characteristics that may moderate healthy lifestyle behaviors, psychosocial health, and birth and post-natal outcomes (e.g., race/ethnicity, income, age, parity, language, level of education, marital status).

**Research Question:** What is the short and long-term effect of the COPE-P program in high-risk pregnant minority women receiving prenatal care on healthy lifestyle behaviors (nutrition and exercise), psychosocial health (healthy lifestyle beliefs, healthy lifestyle behaviors, anxiety, stress and depression), and birth and post-natal outcomes (gestational age at birth, gender, birth weight, birth length, overall health, mode of delivery, breastfeeding (initiation and duration) versus an attention control group (PregnancyPlus group).

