**Table 1. Study Variables, Measures and Timing**

Variables	Measures	Timing
Demographic Characteristics Age, Height Education Level, Relationship Status, Race/Ethnicity, Language Spoken, Income, Parity, Medications, Mental Health Referral/Rx post screening	Demographic and Personal Information (DPI) Form	T0 =Baseline (screening visit) T1 = 31 weeks T2 = 6-8 weeks postpartum visit T3 =6 months well baby visit
Healthy Lifestyle Behaviors	Healthy Lifestyle Behaviors Scale 	T0, T1, T2, T3
Healthy Lifestyle Beliefs	Healthy Lifestyle Beliefs Scale 	T0, T1, T2, T3
Nutrition	24 Hour Nutrition Log/Food Processor	T0, T1, T2, T3
Weight Gain/Loss, BMI	Scale	T0, T1, T2, T3
Exercise	Steps Fitbit Flex 2 Accelerometer	T0 (given at screening T1, T2, T3)
Psychosocial Health		
Anxiety	GAD7	T0, T1, T2, T3
Depressive Symptoms	EPDS	T0, T1, T2, T3
Perceived Stress	PSS	T0, T1, T2, T3
Birth and Post-Natal Outcomes	Infant Data Form	
Gestational Age at birth, Gender	Chart review	Post delivery
Birth Weight, Birth Length, Overall Health	Chart review	Post delivery
Mode of Delivery (C/S, Vaginal, Forceps/Vacuum)	Chart review	Post delivery
Breastfeeding (initiation and duration)	DPI Form	T2, T3
COPE-P Acceptability	Index (COPE-P group)	T1 and T2
Group Prenatal Care Acceptability	Group Prenatal Care Acceptability	T1
Program Experience	COPE-P/PregnancyPlus Program Evaluation	T1 and T3

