**Hypothesis-driven analyses.** Various bivariate tests (e.g., independent and dependent t-tests, correlations, ANCOVA and repeated measures analyses of covariance) will be used to evaluate differences and longitudinal patterns of change across time and between relevant subgroups (e.g., intervention groups, language groups) for each significant outcome in the preliminary bivariate analyses, (primary outcomes are healthy lifestyle behaviors, anxiety, stress, and depressive symptoms). For secondary outcomes (appropriate weight gain during pregnancy, birth and post-natal outcomes (e.g., mode of delivery, birth weight/length, gestational age, postpartum weight loss and breastfeeding practices) we will fit a series of longitudinal multilevel growth models to the data.

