For all continuous outcomes, such as anxiety, the basic model, to which we can add our controls and predictors. The level 1 submodel estimates how each participant's anxiety changes over the four data collection periods. The level 2 submodel will relate the inter-individual differences to intervention group and other time-invariant predictors and controls, such as medication (i.e., antidepressants) and have begun therapy (i.e., in usual care for mental health diagnoses), and will estimate a participant's initial anxiety level and rate of change in anxiety. Anxiety will be modeled in terms of random subject effects (intercept and time trends) to account for individual differences in how participants change over time. We will begin with a linear model for time but will investigate nonlinear effects as suggested by the data. Subsequent models will contain time-varying covariates (i.e., dose of intervention, weight, exercise) and thus will focus on within-participants effects, that is, whether within-participant differences in the covariates are associated with within-participant differences in anxiety. We will examine the potential of cognitive beliefs and perceived difficulty in leading a healthy lifestyle in mediating the effects of the COPE-P program on healthy lifestyle behaviors and psychological symptoms. Rather than detecting mediated effects with the causal steps approach of Baron and Kenny, we will use the Joint Significance Test established by MacKinnon, which assesses the statistical significance of the X to M relation,  $\alpha$  path, and then the M to Y relation,  $\beta$  path. If both are statistically significant, there is evidence of mediation. Models with more than one mediator are simply extensions of the single-mediator case. In our multilevel models, we will investigate mediation effects within the different levels of analysis and across levels. Finally, we will explore characteristics that may moderate healthy lifestyle behaviors, psychosocial health, and birth outcomes (e.g., race/ethnicity, age, parity, language spoken, level of education, income, marital status) in the above models. The proposed examination of mediators and moderators should allow for increased understanding of mechanisms underlying any intervention effect and different responses among the participants. The most appropriate covariance structure for the residuals  $\epsilon_{ij}$  will be determined after data collection and the correlation of responses over time is estimated. Several covariance structures will be examined and the resulting models compared for fit using the quasi-likelihood independence model information criterion (QIC) fit using SAS 9.4 (Proc MIXED).

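### The plan's growth model for pregnancy weight gain and postpartum weight loss runs one time trend across delivery and fixes no arm contrast for either outcome

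*Combined protocol and SAP*

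**What the plan says.** Hypothesis 1b (Aims) predicts that "COPE-P participants will demonstrate more appropriate pregnancy weight gain" and, as a further item, more appropriate weight loss after birth. What counts as appropriate is not defined.

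Under Hypothesis-driven analyses, the Analysis plan covers these outcomes in one sentence. It opens "For secondary outcomes (appropriate weight gain during pregnancy, birth and post-natal outcomes", goes on to list postpartum weight loss, and ends "we will fit a series of longitudinal multilevel growth models to the data".

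The next paragraph gives the general model. It begins "For all continuous outcomes, such as anxiety, the basic model, to which we can add our controls and predictors" and, with anxiety as the example, describes how each participant's outcome "changes over the four data collection periods", with a random intercept and random time trend. On the form of time it says "We will begin with a linear model for time but will investigate nonlinear effects as suggested by the data". The residual covariance structure is to be chosen after data collection.

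Table 1 lists "Weight Gain/Loss, BMI" by scale at T0, T1, T2 and T3. No weight at delivery is listed. The plan states no phase-specific contrast, categorical visit or break at delivery for weight.

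**The concern.** Weight rises through pregnancy, drops at birth and then changes slowly. The two hypotheses concern different parts of that path and point in opposite directions. One trend fitted through T0-T3 mixes them, and most of its information comes from comparing T3 with T0. If the arm difference in that trend were read as the effect on weight, a real difference in pregnancy gain could be heavily diluted, and a difference in postpartum loss could be reported where none exists.

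The provision for nonlinear terms does not settle this. It leaves the form of the curve, and so the quantity compared between arms, to be chosen after the data are seen. Two named secondary outcomes would then have no fixed estimand.

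**Working it through.** **Inputs.** T0 is before 19 weeks (16 assumed) and T1 is at about 31 weeks. T2 is 4-6 weeks postpartum in the text (6-8 in Table 1). T3 is 6 months postpartum. Birth is assumed at 40 weeks, which puts T2 at week 45 and T3 at week 66. All kilogram values below are assumed for illustration.

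**The plan's own time axis.** Months after the end of the intervention = (40 − 31 + weeks postpartum) × 7/30.44.
- T2: 13 × 7/30.44 = 3.0 and 15 × 7/30.44 = 3.4 months (plan: 3).
- T3: 35 × 7/30.44 = 8.0 months (plan: 8).

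The assumed axis agrees with the plan.

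**Slope weights.** With complete data, independent residuals and a random intercept and slope, the fixed slope is Σ wᵢyᵢ, where wᵢ = (tᵢ − t̄)/Σ(tᵢ − t̄)².
- t̄ = (16 + 31 + 45 + 66)/4 = 39.5.
- Deviations are −23.5, −8.5, +5.5, +26.5; their sum of squares is 1357.
- Weights for T0 to T3 are −0.0173, −0.0063, +0.0041, +0.0195 per week.

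T1, the only post-baseline pregnancy visit, enters with a small negative weight.

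**One slope is neither gain nor loss.**
- Path 70, 78, 73, 71 kg: gain 8/15 = 0.53 kg/week, later loss 2/21 = 0.095 kg/week. The line gives −25/1357 = −0.018 kg/week.
- Path 70, 78, 74, 73 kg: the same gain. The line gives 33.5/1357 = +0.025 kg/week.

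**Arm difference of −2 kg at T1, by what remains at T2 and T3.** The true T0-T1 difference is −2 kg and the true T2-T3 difference is 0 in every row.

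| Effect kept at T2 and T3 | Slope difference (kg/week) | Implied over T0-T1 (× 15 weeks) |
|---|---|---|
| All | −2 × 0.0173 = −0.0346 | −0.52 kg |
| Half | +0.0125 − 0.0236 = −0.0111 | −0.17 kg |
| None | −2 × (−0.0063) = +0.0125 | +0.19 kg |

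In the first row the same line also implies −0.0346 × 21 = −0.73 kg over T2-T3, where there is no difference.

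**When the sign reverses.** If a fraction f remains at both T2 and T3, the slope difference is zero at f = 8.5/(5.5 + 26.5) = 0.27, and the sign is wrong only below that. The threshold is 0.21-0.29 across T0 at 12-18 weeks, T1 at 31-34, T2 at 5-7 weeks postpartum and birth at 38-40 weeks. The T1-only slope then runs from +0.0095 to +0.0142.

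**Dependence on covariance.** With AR(1) residuals (correlation 0.5 to 0.9 between adjacent visits) and no random slope, the T1 weight is −0.0016 to +0.0009. A T1-only effect of −2 kg then gives +0.0032 to −0.0018 kg/week, so the reversal nearly vanishes. The slope is then almost blind to weight at T1.

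**Nonlinear time.** A quadratic returns a T0-T1 difference of −0.59 kg (effect at T1 only) to −1.52 kg (lasting effect), against −2. In the T1-only case it also creates a T2-T3 difference of 0.21 − (−0.91) = +1.1 kg. A cubic or categorical visit has four parameters for four nominal times and returns −2.0 kg exactly. So does a piecewise model with a slope in each phase and a change of level at delivery.

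**The case against.** The strongest reply is that the plan does not commit to the model tested here.

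- *Weight as the response is inferred.* No sentence says that weight at T0-T3 is the dependent variable. Gain and loss are named separately, a series of models is promised, and analytic variables are to be constructed. The same sentence covers mode of delivery and gestational age, which occur once and cannot be growth-modelled, so its wording is loose. This stands as a limit. But if derived change scores were intended, a four-period growth model does not apply to them and the plan still needs to say so. If gain is dichotomized, the plan's logistic model applies instead.
- *The nonlinear provision could admit an adequate form.* This is correct: weight would show obvious curvature, and cubic, piecewise or categorical time all fall within it. A reader might infer that the stated approach could never answer the weight questions, and the documents do not support that. What remains is that the form is left to the data and no arm contrast is named.
- *No sentence says the arm-by-time slope will be reported as the effect on weight.* Also correct. The only sentence that makes the interaction the test of effectiveness belongs to the dichotomized-outcome model and is interpreted for psychological symptoms.
- *ANCOVA is mentioned.* It appears among the tests tied to the primary outcomes; secondary outcomes are then assigned growth models.

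**Conclusion.** The concern holds as a gap in specification with a demonstrable consequence. Read together, the two paragraphs of the analysis plan send weight gain and weight loss to a trend over T0-T3 that begins linear. Under that starting model neither outcome is estimated: a lasting 2 kg reduction appears as about a quarter of its size over T0-T1 (0.52/2 = 0.26). The plan does not fix which later form would replace the line.

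This rests on scale weight being the response, birth at 40 weeks, nominal visit times, complete data and independent residuals. Under AR(1) residuals the T1 visit contributes almost nothing to the slope, so the line still does not estimate pregnancy gain.

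A reader might infer that the model will reverse the sign of a COPE-P effect. That goes too far. Reversal needs less than about 27% of the T1 effect to remain at T2 and T3, and its size depends on a covariance structure not yet chosen. The hypothesis also speaks of more appropriate gain without a stated direction, so a particular sign cannot be called benefit or harm from the documents alone.

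These are secondary outcomes. The primary comparisons are not affected by this point.

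**What to change.** For weight, replace the general growth-model wording with a pre-specified model:

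- State that scale weight is the response, with visit as a categorical factor and T0 weight as baseline. A piecewise model with a break at delivery is an alternative, provided the break allows a change of level. Two lines merely joined at delivery have only three parameters and cannot in general reproduce four visit means.
- Test two arm contrasts separately: T0 to T1 for pregnancy gain, and T2 to T3 for postpartum loss.
- Label the first as gain to about 31 weeks, because Table 1 has no delivery weight. For the same reason, the second omits loss before T2.
- Report T3 relative to T0 as well, labelled as retention, because it is not the postpartum loss named in Hypothesis 1b.
- Adjust for gestational age at T0. Use gestational age at the T1 weighing only in a sensitivity analysis: it is post-randomization, and women who miss that session are measured at a later visit.

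The cost is analysis-plan wording, with the same weights, visits and software. The downside is two weight tests instead of one slope.

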If a woman does screen into the study, she will provide further baseline data at this point. In addition to the screening tools, baseline data will include: demographic and personal information, weight from clinic scale, a 24 hour diet recall, the Healthy Lifestyle Beliefs Scale and the Healthy Lifestyle Behaviors Scale. A participant will then be assigned to the next available group based on fetal gestational age (groups having been scheduled and previously randomized as intervention or control as described above). In the event that group prenatal care is not feasible, the group sessions can be conducted as virtual visits (Zoom or Facetime etc.) or content can be provided in a 1:1 patient to provider setting. Participants will then be given an appointment for their first group prenatal care session and a Fitbit Flex 2, instructions on how to immediately begin using the Fitbit (to provide baseline data that will be uploaded at the first group session) and a Fitbit number (for confidentiality) so that they can compare with other pregnant women. All participants will receive \$30.00 for at the baseline visit (**T0**).

All women in this study will receive 6 sessions of group prenatal care beginning at 16 weeks gestation ( $\pm 2$  week) and ending at 31 weeks ( $\pm 2$  week). At 16 weeks gestation, women receive care every three weeks. The timing of our group prenatal care is designed around prenatal testing to decrease participant burden. We will begin at 16 weeks when all women in care have alpha-fetal protein screening drawn. The second session is at  $19 \pm 2$  week, when women are normally receiving an anatomy sonogram. The third session is  $22 \pm 2$  weeks, which is not associated with any specific prenatal care milestones. The fourth session is  $25 \pm 2$  week is associated with third trimester labs and the glucose tolerance test. The fifth session at  $28 \pm 2$  weeks and the sixth session at  $31 \pm 2$  week are not associated with specific prenatal care milestones. Therefore, 3 of the 6 sessions have standard prenatal testing associated with them (encouraging attendance).

**COPE-P intervention group:** The COPE-P intervention group will receive the COPE-P Intervention over the 6 sessions of group prenatal care. Each session lasting for 1 and a half hours.

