### Procedure.

After meeting inclusion criteria for the study, she will be given screening tools (General Anxiety Scale – GAD-7, Perceived Stress Scale – PSS, and the Edinburgh Postnatal Depression Scale – EPDS) to determine study participation.

If a potential participant scores:

- Greater than or equal to 10 on the General Anxiety Disorder 7-item scale (GAD-7)
- Or greater than or equal to 20 on the Perceived Stress Scale (PSS)
- Or a cut-off score of 10 on the Edinburgh Postnatal Depression Scale (EPDS)

They will be eligible to participate in the study. For the GAD-7 a score of  $\geq$  to 10 indicates moderate anxiety and maximizes sensitivity and specificity, for the PSS, a score of 20 or greater is the high-stress cut-off and a cut-off score of 10 on the EPDS is suggested to indicate moderate depressive symptoms in pregnant women.

If a **participant does not screen** into the study, she will be thanked for her time and interest and paid \$10.00 for her participation in the screening process.

07/30/2021

If a **participant does screen into the study**, she will provide further baseline data at this point which includes: demographic and personal information, weight from clinic scale, a 24 hour diet recall, the Healthy Lifestyle Beliefs Scale and the Healthy Lifestyle Behaviors Scale.

A participant will then be assigned to the next available group based on fetal gestational age (groups having been scheduled and previously randomized as intervention or control as described above). Participants will then be given an appointment for their first group prenatal care session and a Fitbit Flex 2, with instructions on how to immediately begin using the Fitbit (to provide baseline data that will be uploaded at the first group session) and a Fitbit number (for confidentiality) so that they can compare with other pregnant women. All participants will receive \$30.00 for at the baseline visit, **T0**.

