All women in this study will receive 6 sessions of group prenatal care beginning at 16 weeks gestation ( $\pm 2$  week) and ending at 31 weeks ( $\pm 2$  week) according to previously described randomization into COPE-P intervention group or PregnancyPlus attention control group. In the event that group prenatal care is not feasible, the group sessions can be conducted as virtual visits (using programs such as Zoom, WebEx, Facetime etc.) or content can be provided in a 1:1 patient to provider setting. Different care providers will deliver the COPE-P and PregnancyPlus content, assuring that there is no carryover effect of the intervention into the control group. [name] will conduct the training of the attention control group midwives and [name] will conduct the training of the intervention group midwives. The same protocol for assessing fidelity will be used for COPE-P and PregnancyPlus. [name] will train the research team to assess fidelity of the intervention with the intervention fidelity checklist. Fidelity will be assessed by having research team members observe 2 of the 6 sessions for each intervention group. Inter-rater reliability of 90% will be established and observer drift monitored and corrected throughout the trial. Feedback will be provided immediately after the session to interventionists if they are not adhering to the intervention as intended to be delivered.

At the end of the 18-week timeframe and at their last group prenatal care session, all women will complete the GAD-7, PSS, EPDS, a 24 hour diet recall, the Healthy Lifestyle Behaviors Scale and the Healthy Lifestyle Beliefs Scale. Fitbit data and weight also will be obtained. In the intervention group, participants also will complete the COPE-P evaluation. This data will be **T1**, and will be collected at approximately 31 weeks gestational age. For women who miss this visit, data will be collected at the next scheduled prenatal visit. Participants will be compensated \$30 for their study participation.

Data collection at the 3 month post intervention follow up visit, **T2**, will occur at the normally scheduled 4-6 weeks regular postpartum visit. Participants will be compensated \$40 for their study participation at this visit. All measures will be collected.

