The 8 month post-intervention visit, **T3**, will be the final data collection point and will occur at a routinely scheduled 6 month well baby visit. Participants will receive \$50 for their participation. All measures will be collected.

A research team member will administer the post-intervention follow-up study questionnaires for each data collection point (T0 – T3). It will be noted how many sessions were completed by the participant. Outcome data from charts will be collected by team members blind to group assignment.

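### Dose of intervention is planned as a time-varying covariate, but all sessions fall between T0 and T1, so with linear time its coefficient can absorb regression to the mean in the three screening scales

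*Combined protocol and SAP*

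**What the plan says.** Under Hypothesis-driven analyses, the model for continuous outcomes has a random intercept and random time trend for each woman. On the form of time: "We will begin with a linear model for time but will investigate nonlinear effects as suggested by the data". Later models add covariates: "Subsequent models will contain time-varying covariates (i.e., dose of intervention, weight, exercise) and thus will focus on within-participants effects". Their coefficients are read as within-woman associations with the outcome.

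Dose is not defined or coded. The only attendance measure is in the Procedure section: "It will be noted how many sessions were completed by the participant".

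On timing, the Procedure section states: "All women in this study will receive 6 sessions of group prenatal care beginning at 16 weeks gestation", ending at about 31 weeks. T0 is the screening visit, and the appointment for the first session is given only afterwards. T1 coincides with the end of the programme: "At the end of the 18-week timeframe and at their last group prenatal care session, all women will complete the GAD-7, PSS, EPDS". T2 and T3 follow at about 3 and 8 months after the intervention, with no further sessions.

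On entry, a woman qualifies on any one of three scales. The first criterion is "Greater than or equal to 10 on the General Anxiety Disorder 7-item scale (GAD-7"; the others are PSS of 20 or more and an EPDS cut-off of 10. The design overview makes the same scores the baseline: "In addition to the screening tools, baseline data will include: demographic and personal information". Anxiety, stress and depressive symptoms are three of the four primary outcomes.

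**The concern.** A within-woman coefficient needs a covariate that varies within a woman in a way that can be separated from time. Cumulative sessions completed vary only once, between T0 and T1. At that same point, scores that had to be high for entry drift back towards each woman's usual level. If the time term is a straight line, part of this fall is left over, and a covariate shaped like the step picks it up.

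The trial could then report that more sessions go with fewer symptoms when the programme does nothing. Attendance is also self-selected, so even a well-fitted dose coefficient would not be a causal dose-response.

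**Working it through.** The plan gives no figure for the dose analysis, so there is none to reproduce.

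**Inputs from the documents.** 364 completers (182 + 182), 1:1 allocation, four visits, six sessions all between T0 and T1, entry on any of three scales, about half screened out, alpha .05.

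**Assumptions not in the documents.** Visits coded 0–3; within-woman correlation (ICC) 0.4, 0.6 or 0.8; correlation 0.6 between true scores on the three scales; attendance Binomial(6, 0.75); no dropout or group clustering; two-sided test.

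**Step 1: what dose can be.** Coded as a total, it is constant, and no within-woman effect can be estimated. Coded cumulatively, it is n × s with s = (0, 1, 1, 1).

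**Step 2: what a straight line leaves behind.** Take t = (0, 1, 2, 3) and centre both. Then Σs² = 0.75, Σt² = 5 and Σst = 1.5. The line removes 1.5²/5 = 0.45 of the 0.75, so 0.30 (40% of the step) remains for dose.

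**Step 3: expected spurious coefficient.** Let every woman fall by δ after T0, whatever her attendance. Mean n = 6 × 0.75 = 4.5, and mean n² = 4.5² + 6 × 0.75 × 0.25 = 21.375. In the person-centred least-squares fit, the coefficient per session is

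−δ × (4.5 × 0.30) / (0.75 × 21.375 − 0.45 × 20.25) = −δ × 1.35 / 6.92 = −0.195δ.

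Over six sessions this is −1.17δ. If sessions are counted in COPE-P only and each arm has its own slope, the same algebra applies within COPE-P.

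The simulated null falls were δ = 0.179, 0.116 and 0.063 SD at ICC 0.4, 0.6 and 0.8. The formula gives −0.21, −0.14 and −0.07 SD. The mixed model of Step 4 (set A) gave −0.20, −0.13 and −0.07 SD.

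**Step 4: how often dose is significant with no true effect.** Set A is a REML model with random intercept and slope, 300 trials per cell (Monte Carlo error about 1 to 3 points). Set B is a separate set of null simulations with the same entry rule.

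| Time term, sessions counted | ICC 0.4 | ICC 0.6 | ICC 0.8 |
|---|---|---|---|
| Linear, both arms, set A | 62% | 40% | 25% |
| Linear, both arms, set B | 62% | 50% | 29% |
| Linear, COPE-P only, set A | 34% | 20% | 16% |
| Linear, COPE-P only, set B | 39% | 26% | 15% |
| Categorical by arm, both arms, set A | 5% | 3% | 3% |
| Categorical by arm, COPE-P only, set A | 3% | 3% | 4% |

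Categorical time by arm gave about 5–9% in set B, and 5.5–9.5% in a smaller run of 200 trials at ICC 0.6. Over sets A and B with linear time, the spurious six-session effect ran from about −0.07 to −0.22 SD.

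**Step 5: is regression to the mean the cause?** With no selection at T0 (ICC 0.6), linear time gave 5.3% (both arms) and 8.0% (COPE-P only). The excess therefore comes from selection.

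**Step 6: attendance linked to a woman's course.** Give each woman her own shift after T0 (assumed SD 0.4) and let those who improve attend more (assumed 0.3 log-odds per SD), still with no programme or dose effect. Categorical time by arm then gave 64/75/95% (both arms) and 35/48/76% (COPE-P only) at ICC 0.4/0.6/0.8. Half that link gave 16–45%. A link to the T0 score instead (ICC 0.6) left categorical time at 3–5%.

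**The case against.** **The plan does not commit to linear time.** It allows nonlinear terms if the data suggest them. This stands in part. Switching to categorical time when a 2-df Wald test rejects linearity cut the error to 9–12% (both arms) and 5–8% (COPE-P only). But the plan gives no rule and no nonlinear form. The test rejected linearity in only 62/39/23% of trials, and quadratic time still gave 7.5–13% at ICC 0.6.

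**A reader might infer that a false dose effect is nearly certain and large.** Entry on one scale alone (assumed mean 8, SD 5, cut-off 10), with linear time kept, gives 99–100% false positives and 2 to 3 points over six sessions, about 0.4–0.65 SD. The documents do not support that setting. It admits about 34% of women, whereas they expect about half to screen in, on any of three scales. In that setting linearity was also rejected in every trial, and categorical time then gave 4–6%.

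**A reader might also infer that the trial's main conclusion is at risk.** It is not. No aim or hypothesis concerns dose, and the analysis principle is intention to treat. The effectiveness test written out for dichotomised outcomes is COPE-P by time. The plan speaks of association and announces no claim about stopping early.

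**Definition and self-selection.** Taking dose as sessions completed is an inference, though no other measure is planned. A mixed model could still estimate a between-woman coefficient for a constant total, but that is not the effect the plan describes. The link between attendance and improvement in Step 6 is assumed, not documented; it shows sensitivity, not a measured bias.

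**Conclusion.** The concern holds for the follow-on dose model. For anxiety, stress and depressive symptoms, the starting linear-time specification confounds dose with the T0-to-T1 step and can credit regression to the mean to attendance. With no true effect, the error rate is about 25–62% (both arms) or 15–39% (COPE-P only), against a nominal 5%. These rates rest on the assumed ICC of 0.8 to 0.4, the assumed attendance and equally spaced visits.

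Categorical time by arm removes this artefact to within about 5–9% (as low as 3% in set A) if attendance is unrelated to a woman's course. It does not protect against self-selected attendance. Healthy Lifestyle Behaviors is not a screening scale, so this mechanism does not reach it directly. The randomised COPE-P by time comparison, fitted without dose, is untouched.

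**What to change.** In the continuous-outcome paragraph of the Analysis plan, delete dose of intervention from the time-varying covariates.

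If it is kept:

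- define it as sessions completed, and state whether PregnancyPlus sessions count;
- fit it with categorical time by arm, not linear time;
- report it as exploratory and associational, with no dose-response claim.

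Optionally, an exploratory analysis of sessions received could use randomised arm as the instrument at T1, T2 and T3, adjusted for the T0 score. It should account for groups, not women, being randomised. It also assumes that arm acts only through sessions, which is open to question because different providers run the two arms.

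The cost is plan wording and a little analysis time on data already collected. The price of keeping dose in this form is a wider interval for its coefficient and a weaker statement about attendance.
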